# **15.13** Data management

Data collection, statistical analysis and preparation of the study report are activities firewalled from vaccine companies to avoid perception of undue influence on the study report and CVE results interpretation.

#### 15.13.1 Data management at site level

Each study site is responsible for the data collection, data validation, and data management of their participant-level study data. Depending on the study site, the data collection and source documentation will be different. For every participating study site, the data flow and data management will be documented in detail, including data collection, validation, data entry and data cleaning processes.

All pseudonymised participant-level study data will be locally transformed to the study-specific common minimum dataset (see Annex 4). The study site will perform quality checks and process any findings accordingly, with sufficient documentation to ensure transparency and reproducibility.

[figure not shown]
When the performed data quality checks are satisfactory, the study site can upload the data. (Section 15.13.2).

### 15.13.2 Data transfer and management at central level

The study-specific common minimum dataset will be uploaded by the study sites to a dedicated secured central server, the COVIDRIVE Research Server (CRS). The server is hosted by P95, [name]. P95 will act as Data Processor according to the General Data Protection Regulation (GDPR) 2016/679. The data flow from the study to the CRS and extraction of results from the CRS is described in Figure 1.

- 1. Each data site will upload the study-specific common minimum dataset through the COVIDRIVE Electronic Data Transfer Application (EDTA), a password-protected secure web application using a secure file transfer protocol (sFTP).
- 2. The CRS system administrator, a certified Data Protection Officer (DPO), checks whether the data are compliant to the protocol, statistical analysis plan (SAP) and privacy regulations.
  - a. If the check is satisfactory, the system administrator releases the uploaded data to the study folder accessible to the data analysts (using Remote Desktop Protocol (RDP)) and performs a data lock (the data are only readable by the data analysts and cannot be changed).
  - b. If the check is not satisfactory, the system administrator reports this to the study site responsible for the data.
- 3. The data analysts perform the required data transformations on the data released in the study folder as per the SAP.
- 4. When the data transformations are finalized, the data analysts flag the resulting output files to the system administrator for extraction out of the CRS. These output files only contain aggregated summary data such as figures, tables with number of events, or estimates.
- 5. The system administrator checks the resulting output files flagged for extraction for compliance to the SAP.
  - a. If the check is satisfactory, the resulting files are extracted out of the CRS by the system administrator using sFTP.
  - b. If the check is not satisfactory, the system administrator reports this to the data analyst and requests changes to get the data into compliance with the SAP.
- 6. After the resulting files are extracted from the CRS, they can be used as the basis for reports, web applications and publications-as per the SAP.

#### Figure 1. Data flow from study sites to the COVIDRIVE research server and beyond.

A data management plan (DMP) is written prior to the start of the data collection to describe data management at the central level. The DMP describes all functions, processes, responsibilities and specifications for data collection, data storage, quality checking, transfer, cleaning, and validation. The DMP is updated regularly.

# 15.14 Data analysis

A full SAP and mock report will be developed prior to the conduct of the analysis. The SAP specifies the statistical analyses to be conducted while the mock report, including tables, figures, and listings (TFL) mock shells, specifies the presentation of the results.

All statistical analyses will take place in the data analysis compartment of the CRS.

#### 15.14.1 Description of SARS-CoV-2 dynamics and COVID-19 vaccine coverage

Context information will be provided by describing the evolution of the SARS-CoV-2 dynamics during the study period in the countries where the study sites are located. The circulating genetic variants will be described as well.

National (or regional) COVID-19 immunisation recommendations over time will be described, along with the coverage of COVID-19 vaccination, overall and by brands of interest.

# Table 7. Sources for context information on circulating genetic variants and national/regionalCOVID-19 immunisation recommendations.

Genetic variants	
« Country 1 »	« link »
« Country 2 »	« link »
COVID-19 immunisation recommenda	itions
« Country 1 »	« link »
« Country 2 »	« link »

#### 15.14.2 Attrition diagram

For every study site, an attrition diagram will be created. The attrition diagram describes the number of records excluded from the statistical analyses, by reason of exclusion. For every study site, a bar chart of the distribution of vaccine brands will be created after exclusion criteria have been applied.

# 15.14.3 Descriptive analysis of demographics and baseline characteristics

For every study site and brand of interest, visualisations based on the final brand-specific data for analysis will be created including:

- number of controls and COVID-19 cases (possibly by genetic variants) over time.
- distribution of covariates among cases and controls.

For every study site and brand of interest, a tabular summary based on the final brand-specific data for analysis will be created, describing the characteristics of cases and controls as predefined in the mock report. Similar visualisations and tabular summaries will be made for the combined data across study sites.

# 15.14.4 Statistical analyses

# 15.14.4.1 Site-specific CVE

For every study site, the crude and confounder-adjusted brand-specific CVE against laboratoryconfirmed COVID-19 disease will be estimated as:

VE = (1 – OR) x 100%,

CINICRIVE

where *OR* denotes the crude or confounder-adjusted odds ratio, comparing the odds of vaccination among COVID-19-positive study participants to the odds of vaccination among COVID-19-negative study participants.

Confounder-adjusted CVE estimates will be derived from multivariable logistic regression models. The analysis to estimate brand-specific CVE will account for the differences in approved indications, discarding from the analysis patients for which the vaccine brand of interest is not indicated. All CVE estimates will be adjusted for calendar time.

# 15.14.4.2 Pooled CVE

Brand-specific CVE estimates pooled across study sites will be obtained through random-effects metaanalysis (RE-MA) on the log-transformed site-specific estimates [12], or alternatively, when cell counts are too low (i.e. resulting in non-robust RE-MA standard error estimates), Generalised Estimating Equations (GEE) will be used [13]. Cell counts are expected to be low when the vaccine effectiveness is very high and/or the proportion of the vaccination coverage covered by the brand of interest is low.

# 15.14.4.2.1 Random effects meta-analysis

Site-specific CVE estimates by vaccine brand will be calculated and these will be pooled through a RE-MA. The main analysis will be based on this two-stage pooling methodology meaning that CVE estimates will be obtained for each site and subsequently pooled. An overview of the analysis workflow can be found in Figure 2.**Fout! Verwijzingsbron niet gevonden.** 

The two-stage pooling approach has the advantage that it can easily integrate estimates from sites that cannot share patient-level data. Additionally, two-stage pooling approaches are easily understood by and communicated to researchers in the field who tend to be familiar with metaanalyses of aggregated data [14]. Finally, note that it has been shown that in most scenarios two-stage and one-stage pooling tend to lead to similar results [14-16]. To account for potential treatment effect heterogeneity, a random effect will be incorporated into the model. Potential causes of such heterogeneity could include differences at the recruitment stage, local differences in the intensity of the epidemic, etc. The most important limitations of the RE-MA approach include loss of power when there is no between-study heterogeneity as compared to a fixed-effects approach, a potential loss of power as compared to a one-stage pooling approach, and potential convergence issues when the outcome of interest is rare or the sample size of some sites is relatively small [16]. One-stage pooling is to be preferred when most, if not all, the sites have shared individual patient data; and additionally, when the number of clusters as well as the total sample size of the study are low, as this leads to more efficient estimates compared to two-stage methods. However, two-stage pooling will be performed as a sensitivity analysis.

**C VIDRIVE** 

[figure not shown]

Figure 2. Analysis workflow from the site-specific datasets to the final CVE estimate.

For the RE-MA models, restricted maximum likelihood will be used to obtain the pooled meta-analyses estimates and 95% CIs [17]. The modified Hartung-Knapp correction will be used to estimate the variance of the mean effect [18]. The estimates and 95% CIs will then be back-transformed to obtain the pooled CVE estimates and 95% CI. An indication for the heterogeneity among estimates from different study sites will be obtained by calculating  $I^2$  according to Higgins et al. [19]. For every meta-analysis performed, the potential impact of outliers and influential estimates on the pooled estimate will be evaluated. Studentised deleted residuals *r* will be used to identify outliers in the meta-analysis. The standardised DFBETAs statistic will be used to identify influential estimates [20].

# 15.14.4.2.2 Generalized Estimating Equations

For the GEE models, the approach for fitting logistic regression developed by Liang and Zeger [21] will be used, assuming an exchangeable correlation matrix to account for potential within-cluster homogeneity in outcomes. The robust sandwich estimator [22] will be used to estimate the standard error of the marginal effect estimates. Clusters will be defined at hospital-level or hospital network-level, depending on the similarities of the hospitals belonging to the same network.

# 15.14.4.3 Pooled relative CVE

The crude and confounder-adjusted brand-specific relative CVE (rVE) against hospitalisation due to laboratory-confirmed COVID-19 disease of the additional dose as compared to an appropriately selected comparator group (see below) will be estimated, as:

$$rVE = (1 - OR) \times 100\%,$$

where *OR* denotes the crude or confounder-adjusted odds ratio, comparing the odds of hospitalisation due SARS-CoV-2 infection among subjects receiving the last additional dose of interest, to the odds of hospitalisation due SARS-CoV-2 infection among subjects who were part of the comparator group.

All CVE estimates will be adjusted for calendar time. Confounder-adjusted CVE estimates will consider additional factors such as age, sex, and chronic conditions. Adjustments will be achieved through inclusion of the relevant terms in the logistic regression models. The smooth functions of age and symptom onset date will be modelled by penalised cubic regression splines and estimated using restricted maximum likelihood for smoothness selection [23].

Brand-specific CVE as additional dose against laboratory-confirmed COVID-19 disease will be estimated by comparing SARI patients with the additional dose (P+N doses) to SARI patients without this last additional dose (P+N-1 doses), but who are eligible to receive the last additional dose, and to unvaccinated SARI patients who are eligible to receive the additional dose (Unvacc) (Figure 3). This will be done for each P+N (P+1, P+2 etc.) separately.

[figure not shown]

Figure 3. Estimation of CVE of N (number of) additional doses compared to unvaccinated and N-1 additional doses, in which P is primary series and all control groups are eligible for the exposure of interest.

For co-primary objective 3, a pooled VEa and VEb, representing the VE of the most recent additional dose of interest, will be obtained. For the pooled analyses, matched comparator groups will be constructed, for each SARI patient receiving a dose of the brand of interest as the most recent additional dose, selecting SARI patients who were unvaccinated or did not receive the last additional dose but who are eligible to receive the additional dose. To support the interpretation of objective 3,

also a pooled VEc across brands representing the VE of the vaccinated comparator group as compared to the unvaccinated comparator group will be presented (co-primary objective 4).

For secondary objective 3 on the time between last and additional dose analyses, two separate analyses will be performed. In the first analysis, time between doses will be treated as the exposure variable binned into categories. In the second analysis, the exposure variable will be a spline function of the time between doses with knots placed at prespecified time points.

For secondary objective 3 on the number of additional doses, the VEa and VEb will be reported by number of doses. The same will be done for VEc as to support the interpretation of secondary objective 3, as is described in secondary objective 4.

Each combination of COVID-19 vaccine dose will be classified as primary (P) or additional dose (N) by expert consensus.

#### 15.14.4.4 Missing values

As COVID-19 status is part of the initial data collection, it is expected that exposure should be known for essentially all subjects. Data on exposure and especially the potential confounders, however, are likely to be missing for a proportion of the subjects. These data are often collected from existing medical records, vaccine registries, etc. which existed before the SARI episode, and it seems reasonable to assume that whether the data is missing is independent of the COVID-19 status during the SARI episode. Assuming that the described missing data mechanism holds, performing a complete case analysis (CCA) will not lead to biased results. The primary analysis will therefore be a CCA, dropping records with missing information for the outcome, exposure of interest or the covariates. In case >20% of the cases and controls have missing covariate information, CCA is likely to be inefficient and alternatives such as multiple imputation and augmented CCA will be explored.

#### 15.14.4.5 Sensitivity analyses

Multiple sensitivity analyses will be performed. In case the RE-MA approach will be adopted, GEE models will be performed as sensitivity. Additional sensitivity analyses will be conducted, exploring the effect of time between symptom onset and swab data and the effects of different SARI case definitions and exclusion of subjects who have received monoclonal antibodies and other anti-SARS-CoV-2 products for either treatment or pre- or post-exposure prophylaxis prior to hospitalisation if there is significant use thereof in the population. Other sensitivity analysis might be conducted when appropriate. All sensitivity analyses will be pre-specified in the SAP.

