#### **Study limitations**

- Low sensitivity and specificity of the RT-PCR test introduces stronger bias (towards underestimating the effectiveness) in the test-negative case-control design compared to the standard case-control design [5]. This bias with the test-negative design increases with increasing SARS-CoV-2 positivity rates within the SARI patients. This potential bias might be mitigated/explored by shortening the time lag between symptom onset and taking the respiratory sample as the sensitivity of the RT-PCR tests decreases with increasing time lag [6].
- The SARS-CoV-2 positivity rates within the SARI patients varies over time and might be very high during certain calendar months, potentially making it difficult to obtain a sufficient number of controls that allow adjustment for time-varying confounding.
- Subjects at highest risk for severe COVID-19 disease are targeted for vaccination first and might have a higher propensity to self-select for vaccination compared to subjects at lower risk. When not properly controlled for, this will lead to a substantial underestimation of the vaccine effectiveness.
- Most EU countries are implementing COVID-19 booster vaccination programmes, and increasingly heterogeneous vaccination policies are being adopted. Furthermore, additional COVID-19 vaccines are being marketed. The booster programmes and additional vaccine brands may result in complex and heterogenous combinations of COVID-19 vaccine doses. This heterogeneity potentially leads to paucity of study patients exposed to a specific combination of COVID-19 vaccine doses.
- The emergence of monoclonal antibodies and other anti-SARS-CoV-2 antibody products that impact the course of COVID-19 disease might affect the CVE estimates. Thus, confounders such as healthcare-seeking behaviour and chronic conditions might impact both the likelihood of vaccination and of treatment.
- Pre-existing immunity is a factor influencing vaccine effectiveness estimates. Prior natural infection is a typical reason for pre-existing immunity, however prior infections may be undocumented. A careful interpretation of all time-related effects will be warranted.

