#### 15.6.2 SARI patient (possible COVID-19 cases)

A possible COVID-19 case is defined as a hospitalised person with a suspicion of a respiratory infection with **at least one** of the following symptoms:

- cough
- fever
- shortness of breath
- sudden onset of anosmia, ageusia or dysgeusia

with symptom onset within the last 14 days prior to hospital admission as per ECDC definition [10].

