#### 15.6.3 Test-positive case

A study participant who:

• meets the SARI case definition (see Section 15.6.2)

AND

tests positive in at least one SARS-CoV-2 RT-PCR or similar molecular assays with specimen(s) collected between 14 days prior to and up to [72 hours] after hospital admission.

 72 hours after hospital admission is the maximum delay accepted for testing. Each brand-specific protocol will specify whether the study uses a delay of 24 hours, 48 hours or 72 hours after admission.

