#### 15.6.4 Test-negative control

A study participant that:

• meets the SARI case definition (see 15.6.2)

AND

tests negative for all SARS-CoV-2 RT-PCR or similar molecular assays with specimen(s) collected between 14 days prior to and up to [72 hours] after hospital admission.. Test-negative controls must have a negative result for the RT-PCR or similar molecular assay within [72h] of hospital admission.

 72 hours after hospital admission is the maximum delay accepted for testing. The brand-specific protocol will specify whether the study uses a delay of 24 hours, 48 hours or 72 hours after admission.

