post_prophylaxis_ brand	Brand of latest received anti-SARS-CoV- 2 antibody product or other drugs indicated for post-exposure prophylaxis for SARS-CoV-2 infection	Numeric (categorical)	0=Kineret (anakinra)* 1=Regkirona (regdanvimab) 2=RoActemra (tocilizumab) 3=Ronapreve (casirivimab / imdevimab) 4=Veklury (remdesivir) 5=Xevudy (sotrovimab)

			COVIDRIV
			6=Evusheld (tixagevimab / cilgavimab) 7=Lagevrio (molnupiravir) 8=Paxlovid (PF-07321332 / ritonavir) 9=Other
post_prophylaxis_ date	Date of treatment start latest received anti-SARS-CoV-2 antibody product or other drugs indicated for post-exposure prophylaxis for SARS-CoV-2 infection	DD/MM/YYYY	
post_symptom	Having received anti-SARS-CoV-2 antibody products or antiviral drugs indicated for treatment post-symptom onset leading to current hospitalisation	Binary	0=No 1=Yes 9999=No information
post_symptom_br and	Brand of received anti-SARS-CoV-2 antibody products or antiviral drugs indicated for treatment post-symptom onset prior leading to current hospitalisation	Numeric (categorical)	0=Kineret (anakinra)* 1=Regkirona (regdanvimab) 2=RoActemra (tocilizumab) 3=Ronapreve (casirivimab / imdevimab) 4=Veklury (remdesivir) 5=Xevudy (sotrovimab) 6=Evusheld (tixagevimab / cilgavimab) 7=Lagevrio (molnupiravir) 8=Paxlovid (PF-07321332 / ritonavir) 9=Other
post_symptom_da te	Date of treatment start anti-SARS-CoV-2 antibody products or antiviral drugs indicated for treatment post-symptom onset leading to current hospitalisation	DD/MM/YYYY	

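### The planned exclusion of patients treated for SARS-CoV-2 after symptom onset removes mainly cases, so this sensitivity analysis can shift CVE when treatment uptake differs by vaccination status

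*Protocol*

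**What the plan says.** Section 15.14.4.5 of the protocol lists, among the sensitivity analyses to be conducted, "exclusion of subjects who have received monoclonal antibodies and other anti-SARS-CoV-2 products for either treatment or pre- or post-exposure prophylaxis prior to hospitalisation". It applies "if there is significant use thereof in the population", with no threshold given. The same section leaves pre-specification of all sensitivity analyses to the SAP.

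Annex 4 (Treatments) records three uses in separate fields, each with a start date: `pre_prophylaxis_6mo`, `post_prophylaxis_6mo` and `post_symptom`. The last is defined as "Having received anti-SARS-CoV-2 antibody products or antiviral drugs indicated for treatment post-symptom onset leading to current hospitalisation". Table 3 in Section 15.10 has the same three-way split.

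Three definitions fix who is a case and who is a control:
- A SARI patient (15.6.2) qualifies "with symptom onset within the last 14 days prior to hospital admission".
- A test-positive case (15.6.3) "tests positive in at least one SARS-CoV-2 RT-PCR or similar molecular assays with specimen(s) collected between 14 days prior to and up to" at most 72 hours after admission.
- A test-negative control (15.6.4) "tests negative for all SARS-CoV-2 RT-PCR or similar molecular assays with specimen(s) collected between 14 days prior to and up to" the same limit.

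Section 15.14.4.1 defines CVE as (1 − OR) × 100%, with the OR "comparing the odds of vaccination among COVID-19-positive study participants to the odds of vaccination among COVID-19-negative study participants". The limitations in the abstract add that "confounders such as healthcare-seeking behaviour and chronic conditions might impact both the likelihood of vaccination and of treatment".

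**The concern.** Pre-exposure prophylaxis is given before infection, so it can occur in future cases and future controls alike. Treatment after symptom onset is different. It is directed at SARS-CoV-2 in the current episode and normally follows a positive test. Onset lies within 14 days before admission, so that test falls in the window that defines a case. Excluding treated patients is then, in large part, selecting on the outcome: vaccinated and unvaccinated cases are thinned at their own treatment rates, while the controls stay nearly intact.

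At stake is how the robustness check is read. A difference between the main and the sensitivity estimate would naturally be taken as the influence of these products on CVE. Part or all of it could come from the exclusion itself. The analysis is run when use is significant, which is also when such an artefact can be largest.

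**Working it through.** The protocol gives no figure for this analysis, so there is none to reproduce.

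**Inputs**
- OR and CVE as in 15.14.4.1.
- True CVE: 80% or 90% (15.11.1.1), and 70% for the comparator group (15.11.1.3).
- t_v and t_u, the treated shares of vaccinated and unvaccinated cases: not in the documents; assumed between 10% and 30%.
- Treated controls: assumed none.

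**Formula**

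Exclusion leaves a fraction (1 − t_v) of vaccinated cases and (1 − t_u) of unvaccinated cases. Controls do not change, so

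OR after exclusion = OR × (1 − t_v)/(1 − t_u).

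**Results for a true CVE of 80% (OR 0.20)**

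| t_v | t_u | OR after exclusion | CVE |
|---|---|---|---|
| 10% | 10% | 0.20 × 0.90/0.90 = 0.200 | 80.0% |
| 20% | 10% | 0.20 × 0.80/0.90 = 0.178 | 82.2% |
| 30% | 10% | 0.20 × 0.70/0.90 = 0.156 | 84.4% |
| 10% | 20% | 0.20 × 0.90/0.80 = 0.225 | 77.5% |
| 10% | 30% | 0.20 × 0.90/0.70 = 0.257 | 74.3% |

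At 90%, uptake of 30% v 10% gives 1 − 0.10 × 0.70/0.90 = 92.2%, and 10% v 30% gives 87.1%. At 70% the same pairs give 76.7% and 61.4%.

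**Check with expected counts**

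This uses the Annex 6 cell formula for the Table 4 row with 1,105 cases (CVE 80%, coverage 60%, 1:1, brand share 10%).
- P(unexposed | case) = 1/(1 + 0.20 × 0.60/0.40) = 0.769, or 850 cases.
- Cases exposed to the brand: 850 × 0.20 × 0.06/0.40 = 25.5.
- Controls: 1,105 × 0.40 = 442 unexposed and 1,105 × 0.06 = 66.3 exposed.
- OR = (25.5/850)/(66.3/442) = 0.03/0.15 = 0.20.
- After excluding 30% of exposed and 10% of unexposed cases: (17.85/765)/0.15 = 0.156, so CVE is 84.4%, as in the table.

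**Does exclusion at least move toward the truth?**

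Let t now be uptake among infected outpatients and e the efficacy of treatment against hospitalisation, with a true CVE of 80% in the absence of treatment.
- Keeping treated cases: OR × (1 − e·t_v)/(1 − e·t_u).
- Excluding them: OR × (1 − t_v)/(1 − t_u).

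With t_v 30%, t_u 10% and e = 50%, keeping gives 1 − 0.20 × 0.85/0.95 = 82.1%, and excluding gives 84.4%. With e = 0, keeping gives 80% and excluding still gives 84.4%. For any e below 100% and unequal uptake, exclusion moves the estimate further from 80%, in the direction of the distortion it is meant to explore.

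**Prophylaxis for comparison**

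If, within each vaccination group, the same share of cases and controls is dropped, the factors cancel and the OR is unchanged.

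**The case against.** The strongest reply is that this is SAP territory: half a sentence, conditional on use, with details deferred, and Annex 4 keeps the three uses apart so they could be run separately. That is fair for thresholds and layout. It does not remove the point, because the protocol already names treatment as a ground for exclusion.

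A reader might infer that the exclusion removes only cases. The documents do not support that. Controls are defined by negative molecular tests alone, so a patient treated on an antigen test or on suspicion can be a control. Section 17 puts PCR clinical sensitivity at 70%–71% on days 9 to 11, so some treated, infected patients may be classed as controls. The `post_symptom` product list also includes anakinra and tocilizumab, which could be recorded in controls. Zero treated controls is a simplification.

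A reader might also infer that the check is biased whenever treatment is common. It is not: the level of uptake does not matter, only the difference between vaccinated and unvaccinated cases. The formula is crude, whereas the planned estimates are adjusted, and a difference fully explained by the adjusted covariates leaves the adjusted OR unchanged. Chronic conditions and influenza and pneumococcal vaccination are collected at all sites and may absorb part of it. Healthcare-seeking behaviour, which the protocol itself names as a shared driver, is not a listed covariate in its own right.

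Finally, keeping treated cases is not neutral either, as the 82.1% above shows. In that example the exclusion adds 2.3 points (84.4 − 82.1).

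**Conclusion.** The point holds in a limited form. Following 15.14.4.5 as written selects largely on the outcome through the post-onset treatment part, and the result can move in either direction. For a true CVE of 80% and uptake differences of 10 to 20 percentage points, the shift runs from −5.7 points (74.3%) to +4.4 points (84.4%); with equal uptake it is zero. These sizes rest on assumed uptake, no treated controls, and a difference that adjustment does not remove. The abstract's limitations make such a difference plausible but do not establish it.

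It would be wrong to conclude that the co-primary CVE estimates are affected. Only a conditional sensitivity analysis is, and the harm is a robustness check that could be misread. Pre-exposure prophylaxis is not the problem. Post-exposure prophylaxis lies in between, because it follows a known exposure and so may itself be linked to becoming a case. The change is worth making before the analysis is run.

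**What to change.** Amend the sentence in 15.14.4.5 and carry it into the SAP:
- Do not exclude on `post_symptom`.
- Base the exclusion on pre-exposure prophylaxis started before symptom onset, using `pre_prophylaxis_6mo` with its start date and the onset date.
- Run any exclusion for post-exposure prophylaxis (`post_prophylaxis_6mo`) as a separate analysis.
- Tabulate post-onset treatment among cases by vaccination status, so that readers can see whether uptake differs.

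All fields are already in Annex 4, so the amendment adds no new data items. The cost is slightly more analysis work, and the sensitivity analysis no longer addresses post-onset treatment by exclusion. With post-onset treatment out of the rule, the factor (1 − t_v)/(1 − t_u) drops out: in the examples above, 80% stays 80% as far as this mechanism goes.
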